## 7.2. Dose Modification

Dose modification is not allowed.

## 7.3. Method of Treatment Assignment

All participants will be centrally assigned to randomized study treatment using an IWRS. Before the study is initiated, the log-in information and directions for the IWRS will be provided to each site.

Study treatment will be dispensed at the study visits summarized in the schedule of activities (Section 2).

Returned study treatment should not be re-dispensed to the participants.

## 7.4. Blinding/Masking

The IWRS will be programmed with blind-breaking instructions. The study blind may be broken if, in the opinion of the investigator, it is in the participant's best interest to know the study treatment assignment. The sponsor must be notified before the blind is broken unless identification of the study treatment is required for a medical emergency in which the knowledge of the specific blinded study treatment will affect the immediate management of the participant's condition (eg, antidote is available). In this case, the sponsor must be notified within 24 hours

after breaking the blind. The date and reason that the blind was broken must be recorded in the source documentation and electronic case report form (eCRF), as applicable.

### **7.5. Preparation/Handling/Storage/Accountability**

1. All study treatment will be provided and shipped to the study centers by Allergan Inc., and must be stored in an appropriate secure area (eg, a locked cabinet in a locked room) at refrigerate conditions (5°C with a permitted range of 2°C-8°C) and must be protected from heat and moisture.
2. The investigator or designee must confirm appropriate temperature conditions have been maintained during transit for all study treatment received and any discrepancies are reported and resolved before use of the study treatment.
3. Only participants enrolled in the study may receive study treatment, and only authorized site staff may supply or administer study treatment. All study treatments must be stored in a secure, environmentally controlled, and monitored (manual or automated) area in accordance with the labeled storage conditions with access limited to the investigator and authorized site staff.
4. The investigator, institution, or the head of the medical institution (where applicable) is responsible for study treatment accountability, reconciliation, and record maintenance (ie, receipt, reconciliation, and final disposition records).
5. Further guidance and information for the final disposition of unused study treatment are provided in the study reference manual.

### **7.6. Treatment Compliance**

Compliance with administration of double-blind study treatment in the clinic at Visits 2, 5, and 8 will be monitored by capturing the date that the participant ingested the double-blind study treatment at each of these visits. If a scheduled ingestion does not occur, the sponsor must be notified and the reason captured in the eCRF.

Compliance with study treatment dosing by the participant outside of the clinic will be monitored by counting the number of tablets dispensed and returned. Before dispensing new study treatment, study center personnel will make every effort to collect all unused study treatment and empty bottles. If a participant demonstrates poor compliance at any time during the study (< 80% or > 120% measured by pill counts), the investigator should evaluate whether the participant should be discontinued from the study.

The study centers will keep an accurate drug disposition record that specifies the amount of study treatment administered to each participant and the date of administration.

## **7.7. Concomitant Therapy**

The use of any concomitant medication, prescription or over-the-counter, is to be recorded on the participant's eCRF at each visit along with the reason the medication is taken.

### **7.7.1. Prohibited Treatments**

Participants must discontinue any of the medications listed below for the specified period prior to baseline. These medications are prohibited for the duration of the study. Other medications being used at screening may be continued.

The following medications are prohibited:

- Antipsychotics
- Antidepressants
- Stimulants
- Anticonvulsants/mood stabilizers
- Dopamine-releasing drugs or dopamine agonists
- Psychotropic drugs not otherwise specified (including herbal products, such as St. John's Wort, and certain nutritional supplements)

See [Appendix 6](#) Concomitant Medications for a comprehensive list of prohibited medications and allowed medication usage. Appropriate washout of prohibited medications is to be conducted at the discretion of the investigator and should begin as soon as practical following consent and screening.

The decision to administer a prohibited medication/treatment during the study period is done with the safety of the study participant as the primary consideration. When possible, the sponsor is to be notified before the prohibited medication/treatment is administered.

### **7.7.2. Permitted Treatments**

Any medication or vaccine (including over-the-counter or prescription medicines, vitamins, and/or herbal supplements) that the participant is receiving at the time of enrollment or receives during the study must be recorded along with:

- Indication
- Dates of administration including start and end dates
- Dosage information including dose and frequency

Therapy considered necessary for the participant's welfare may be given at the discretion of the investigator. If the permissibility of a specific medication/treatment is in question, please contact the sponsor.

The sponsor or designee should be contacted if there are any questions regarding concomitant or prior therapy.

**For Insomnia**

Eszopiclone, zolpidem, zolpidem extended-release, zopiclone or zaleplon for insomnia may be continued provided the medication has been used in a consistent manner for 4 weeks prior to enrollment. Following enrollment, these medications may also be introduced in participants not previously treated as necessitated by insomnia that emerges or worsens during the study. In these participants, the medications will be permitted up to 3 times a week at the following doses (not permitted within 8 hours of efficacy measures):

- Zolpidem (maximum of 10 mg/day)
- Zolpidem extended release (maximum of 12.5 mg/day)
- Zaleplon (maximum of 20 mg/day)
- Eszopiclone (maximum of 3 mg/day)
- Zopiclone (maximum of 7.5 mg/day)
- Suvorexant (maximum of 10 mg/day)

These medications must be administered before bedtime as recommended in their prescribing information. The medication must be documented on the concomitant medications page of the eCRF. No such medication is permitted within 8 hours of psychiatric or neurological assessments.

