  8. Positive result at Visit 1 from the urine drug screen (UDS) test for any prohibited medication. Exception: participants with a positive UDS at Visit 1 for opiates, cannabinoids, or episodic use of benzodiazepines may be allowed in the study provided:

- a. The drug was used for a legitimate medical purpose;
  - b. The drug can be discontinued prior to participation in the study (except for episodic use of benzodiazepines which may be continued); and
  - c. A repeat UDS is negative for these substances prior to enrollment (except for episodic use of benzodiazepines which may be continued)
9. Suicide risk, as determined by meeting any of the following criteria:
- a. A suicide attempt within the past year
  - b. Significant risk, as judged by the investigator, based on the psychiatric interview or information collected in the C-SSRS at Visit 1 (Screening) or Visit 2 (Baseline)
  - c. MADRS Item 10 score  $\geq 5$  at Visit 1 (Screening) or Visit 2 (Baseline) on the MADRS
10. At imminent risk of injuring self or others or causing significant damage to property, as judged by the investigator.
11. Requiring concomitant treatment with any of the prohibited medications, supplements, or herbal products listed in [Appendix 6](#), including any psychotropic drug or any drug with psychotropic activity, except as described in [Section 7.7.2](#).
12. Prior participation in any investigational study of AGN-241751.
13. Initiation or termination of psychotherapy for depression within the 3 months preceding Visit 1, or plans to initiate, terminate, or change such therapy during the course of the study. (Support meetings or counseling [eg, marital counseling] are allowed provided they are no more frequent than weekly and do not have treatment of depression as their objective).
14. Ongoing treatment with phototherapy, or termination of phototherapy within 1 month of Visit 1.
15. Known allergy or sensitivity to the study medication or its components.

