## 12.6. Appendix 6: Concomitant Medications

Therapy considered necessary for the participant's welfare may be given at the discretion of the investigator. If the permissibility of a specific medication/treatment is in question, please contact the sponsor.

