**Medications Allowed (Y) and Medications Not Allowed (N) as Concomitant Medications**

Drug Class	Frequency of Use		Restrictions/Exceptions/Clarifications
	Episodic (PRN)	Chronic	
Psychotropic drugs not otherwise specified (including herbal products)	N	N	No drugs with psychomotor effects or with anxiolytic, antidepressant, stimulant, antipsychotic, or sedative properties are allowed except as stipulated by the protocol. Herbal/dietary products and supplements with potential psychoactive actions, including St. John's wort, ginkgo biloba, kava, SAMe, valerian root, DHEA, tyrosine, tryptophan and 5-HTP are not allowed. Omega-3 supplements are allowed if the dose of EPA is $\leq$ 1000 mg/day, and the participant has been taking same for at least 1 month.
Sedatives/hypnotics	Y	N	Only zolpidem (Ambien up to 10 mg/day and Ambien CR up to 12.5 mg/day), zaleplon (Sonata) up to 20 mg/day, eszopiclone (Lunesta) up to 7.5 mg/day, zopiclone up to 7.5 mg/day, and suvorexant (Belsomra) up to 10 mg/day are permitted, up to 3 times a week, if required for sleep. Sedatives/hypnotics may not be used in the 8 hours before any behavioral assessments.
Steroids, inhalant	Y	Y	
Steroids, intra-articular	Y	N	
Steroids, systemic	N	N	
Steroids, topical	Y	Y	
Vaccines	Y	N	

N = not allowed; PRN = as needed; Y = yes, allowed.

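### Protocol 7.7.2 caps newly started eszopiclone at 3 mg/day, but the Appendix 6 sedatives/hypnotics row allows up to 7.5 mg/day

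*Protocol*

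**What the plan says.** Protocol 7.7.2 (For Insomnia) deals with two groups. Participants who have used one of the named hypnotics consistently for 4 weeks before enrollment may continue it. Participants not previously treated may start one if insomnia emerges or worsens. The dose list belongs to the second group: "In these participants, the medications will be permitted up to 3 times a week at the following doses". The eszopiclone entry in that list reads "Eszopiclone (maximum of 3 mg/day" and the zopiclone entry is 7.5 mg/day.

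The sedatives/hypnotics row of Appendix 6 (section 12.6) gives "eszopiclone (Lunesta) up to 7.5 mg/day, zopiclone up to 7.5 mg/day", and says of all its listed drugs that they "are permitted, up to 3 times a week, if required for sleep". It does not separate newly started from continued use.

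Section 7.7.1 directs the reader to Appendix 6 "Concomitant Medications for a comprehensive list of prohibited medications and allowed medication usage".

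**The concern.** The drug, the purpose and the weekly frequency are the same, but the daily maximum is not. A newly treated participant falls under both entries. A site that looks up eszopiclone in Appendix 6, as 7.7.1 invites it to do, finds a clear limit above the one in 7.7.2 and nothing to suggest a second figure.

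Two things are at stake. First, the protocol gives sites conflicting instructions on an operative dose limit for a sedative. Second, a dose above 3 and up to 7.5 mg/day has no settled status. SAP section 8 lists concomitant medications as a category of important protocol deviations, to be reviewed and documented before database lock and unblinding. It sets no dose check, so whoever does that review would have to choose between the two limits without guidance.

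**Working it through.** No sample-size, power or error-rate formula applies. The check is a line-by-line comparison of the six daily maxima, in mg/day.

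| Drug | Protocol 7.7.2 | Appendix 6 row | Agree? |
|---|---|---|---|
| Zolpidem | 10 | 10 | yes |
| Zolpidem extended release | 12.5 | 12.5 | yes |
| Zaleplon | 20 | 20 | yes |
| Eszopiclone | 3 | 7.5 | **no** |
| Zopiclone | 7.5 | 7.5 | yes |
| Suvorexant | 10 | 10 | yes |

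Five of six agree. For eszopiclone the ratio is 7.5/3 = 2.5 and the difference is 7.5 − 3 = 4.5 mg/day. Both figures are maxima, so a dose of 3 mg/day or less satisfies both, and the disputed range is above 3 and up to 7.5 mg/day.

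Three innocent explanations were tested.

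- **Different populations.** The 7.7.2 list covers newly treated participants only. The Appendix 6 row covers hypnotic use without that split, carries the same limit of 3 times a week, and matches 7.7.2 on every other drug. A separate dose scheme that changed one drug alone would be odd.
- **Superseded text.** Both figures stand in the current body and appendix, and both are legible. Neither the Amendment 1 nor the Amendment 2 summary lists a change to 7.7.2 or Appendix 6, so the documents offer no reason for the difference.
- **A precedence rule.** None is stated for dose. Section 7.7.1 points towards the appendix. Some wording leans the other way. Exclusion criterion 11 bars participants who need prohibited medication, "including any psychotropic drug or any drug with psychotropic activity, except as described in" Section 7.7.2, but that governs eligibility. The psychotropic row of Appendix 6 allows sedative drugs only as the protocol provides, but it covers drugs not otherwise specified, and hypnotics have their own row. Section 7.7.2 also says "These medications must be administered before bedtime as recommended in their prescribing information", which concerns bedtime use. None of these fixes the eszopiclone maximum.

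**The case against.** The strongest reply is that the two limits can be obeyed together, and that safeguards make a problem unlikely. A prescriber would have to rely on the appendix alone and also choose a dose above 3 mg. Section 7.7.2 refers to the prescribing information, dose and frequency must be recorded, and Appendix 6 itself says "If the permissibility of a specific medication/treatment is in question, please contact the sponsor". The lean of exclusion criterion 11 and of the psychotropic row towards the body text adds some weight.

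Much of this stands as a limit on the consequence. It does not remove the discrepancy. Advice to ask when permissibility is in doubt helps only a site that has a doubt, and the appendix entry read alone gives none.

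A reader might go further and infer that participants would be harmed at 7.5 mg/day. The documents do not support that: they give no safety threshold for eszopiclone and no expected rate of hypnotic use, so neither harm nor the number of participants affected can be estimated.

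A reader might also infer a threat to the efficacy comparison. That is not supported either. The Appendix 6 limit is the same for every treatment group. Neither Protocol 10.3 nor SAP section 6 defines a per-protocol set from which such a dose could remove a participant. SAP section 8 only tabulates deviations judged important, and nothing says that this dose would be so judged.

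**Conclusion.** The point holds as a minor internal inconsistency. One of six hypnotic limits differs, 3 against 7.5 mg/day, so that Appendix 6 permits 2.5 times the maximum in 7.7.2 for newly started eszopiclone. The conclusion rests on the current text of both sections and on reading the Appendix 6 row as covering newly treated participants, which its wording does.

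That the 7.5 mg figure was carried over from the adjacent zopiclone entry is plausible, but it is an inference; the documents do not say which figure was intended. What is established is an unclear site instruction and an unclear standard for classifying a deviation. No effect on the primary analysis, no between-arm bias and no quantified harm is claimed.

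**What to change.** Change the eszopiclone limit in the Appendix 6 sedatives/hypnotics row from 7.5 to 3 mg/day, unless the sponsor documents that 7.5 mg was intended (in which case 7.7.2 is the text to correct). Notify sites of the figure that applies.

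There is a small downside. Because the row does not separate new from continued use, a 3 mg/day limit there would also apply to participants continuing prior eszopiclone, for whom 7.7.2 states no dose limit. The row's other five limits already work this way for their drugs. If the sponsor does not want that, a short clause in the row can exempt continuing users. The row also marks chronic use as not allowed, while 7.7.2 lets consistent prior use continue; the one-figure edit leaves that question where it is.

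The cost is one figure, a possible clause and a site notice. Appendix 3 requires ethics approval before amended changes to the study design take effect; the sponsor should confirm whether this correction needs that step or can wait for the next amendment. Sample size, visits, analysis sets and the SAP are unchanged.

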**For Anxiety or Agitation**

Episodic use of benzodiazepines up to approximately 2 mg/day lorazepam equivalent dose and for up to 3 consecutive days at a time may be given for anxiety-related conditions and agitation (not permitted within 8 hours of efficacy assessments).

**7.8. Treatment after the End of the Study**

Participants whose MDD symptoms worsen or are determined by the investigator not to be adequately controlled prior to completing the double-blind treatment period will be allowed to discontinue the study and start appropriate treatment at the investigator's discretion. This new treatment will not be provided by the sponsor.

## **8. Discontinuation/Withdrawal Criteria**

Notification of early participant discontinuation from the study and the reason for discontinuation will be made to the sponsor and will be clearly documented on the appropriate case report form.

Reasons for discontinuation from the study treatment and/or the study may include the following:

- Adverse event
- Lack of efficacy
- Lost to follow-up
- Non-compliance with study drug
- Other
- Pregnancy
- Protocol deviation
- Screen failure
- Site terminated by sponsor
- Study terminated by sponsor
- Withdrawal by subject (withdrawal of consent to participate in the study)

### **8.1. Discontinuation of Study Treatment**

All randomized participants who prematurely discontinue from the study, regardless of cause, should be seen for a final assessment at an ET Visit. A final assessment will be defined as completion of the evaluations scheduled for all participants at Visit 9/ET Visit. Participants who prematurely discontinue from the study before completing 3 weeks of double-blind treatment should enter the 1-week safety follow-up period.

Any participant may be withdrawn due to AE at the discretion of the investigator.

Any participant who meets any of the following criteria at any point during the study must be withdrawn from participation, due to AE(s) related to suicide:

- a) A suicide attempt
- b) Significant risk, as judged by the investigator, based on the psychiatric interview or information collected in the C-SSRS
- c) MADRS Item 10 score  $\geq 5$

In the event that a participant is withdrawn for a suicide-related AE, the participant should be referred for additional treatment or hospitalization, as clinically indicated, in addition to withdrawing the participant from the study.

Discontinuation of study treatment for abnormal liver function (criteria for potential Hy's law described in Section 9.2.6) should be considered by the investigator if the investigator believes that it is in best interest of the participant.

If a clinically significant finding is identified after enrollment, the investigator or qualified designee will determine if the participant can continue in the study and if any change in participant management is needed. Any new clinically relevant finding should be reported as an AE.

See the schedule of activities (Section 2) for data to be collected at the early termination visit and the safety follow-up visit.

## **8.2. Withdrawal from the Study**

- A participant may withdraw from the study at any time at his/her own request, or may be withdrawn at any time at the discretion of the investigator for safety, behavioral, compliance, or administrative reasons.
- If the participant withdraws consent for disclosure of future information, the sponsor may retain and continue to use any data collected before such a withdrawal of consent.
- If a participant withdraws from the study, he/she may request destruction of any samples taken and not tested, and the investigator must document this in the site study records.
- See the schedule of activities for data to be collected at the time of study discontinuation and follow-up and for any further evaluations that need to be completed.

## **8.3. Lost to Follow Up**

A participant will be considered lost to follow-up if he or she repeatedly fails to return for scheduled visits and is unable to be contacted by the study site.

The following actions must be taken if a participant fails to return to the clinic for a required study visit:

- The site must attempt to contact the participant and reschedule the missed visit as soon as possible and counsel the participant on the importance of maintaining the assigned visit schedule and ascertain whether or not the participant wishes to and/or should continue in the study.

- Before a participant is deemed lost to follow up, the investigator or designee must make every effort to regain contact with the participant (where possible, 2 telephone calls, and if necessary, a certified letter to the participant's last known mailing address or local equivalent methods). These contact attempts should be documented in the participant's medical record.
- Should the participant continue to be unreachable, he or she will be considered to have withdrawn from the study with a primary reason of lost to follow-up.

## 9. Study Assessments and Procedures

- Study procedures and their timing are summarized in the schedule of activities (Section 2).
- Protocol waivers or exemptions are not allowed.
- Immediate safety concerns should be discussed with the sponsor immediately upon occurrence or awareness to determine if the participant should continue or discontinue study treatment.
- Adherence to the study design requirements, including those specified in the schedule of activities, is essential and required for study conduct.
- All screening evaluations must be completed and reviewed to confirm that potential participants meet all eligibility criteria. The investigator will maintain a screening log to record details of all participants screened and to confirm eligibility or record reasons for screening failure, as applicable.
- Procedures conducted as part of the participant's routine clinical management (eg, blood count) and obtained before signing of the ICF may be utilized for screening or baseline purposes provided the procedure met the protocol-specified criteria and were performed within the time frame defined in the schedule of activities.
- Repeat or unscheduled blood samples may be taken for safety reasons or for technical issues with the samples.

### Diagnostic Assessments

The SCID will be administered during the screening interviews by a psychiatrist, doctoral-level clinical psychologist, or other clinician who has extensive professional training and experience in the diagnosis of mental illness and who meets the training requirements and qualification standards set by the sponsor and rater training vendor.

Participants will complete a computer-administered Diagnostic Validation (DxV) assessment at Visit 1 (Screening) prior to the rater-administered SCID, on a tablet computer provided to the study center. The DxV will collect data about the participants' history relative to lifelong history of MDD. The participant's diagnostic information, based on the responses to the computerized interview, will be reviewed by the independent clinical reviewers team appointed by the sponsor, and any uncertainty raised by the participant's responses on the diagnostic interview will be discussed with the investigator/study center clinician in order to establish confidence in the diagnosis. Participants for whom diagnostic agreement between the investigator/study center clinician and the rater vendor clinician cannot be reached, may not be appropriate for study participation.

Eligibility of potential participants will be confirmed by agreement with external clinical reviewer (Bracket), in which screening data will be obtained to evaluate psychiatric status (including MADRS, CGI-S, and SCID). Investigators will complete the Clinical Validation Inventory for Study Admission (C-VISA) worksheet as part of the adjudication process. The

SCID and MADRS will be audio recorded at the Visit 1 (Screening). The C-VISA worksheet and SCID and MADRS recordings will be reviewed by a team of independent clinical reviewers appointed by the sponsor.

